Estimand 3B: Difference in mean change from baseline in DAS28-hsCRP in patients with moderate to severe active RA with a previous inadequate response to MTX alone, with confirmed intraarticular synovitis on baseline MRI, after each of 4, 8, and 12 weeks of treatment with MBS2320 (5 mg, 20 mg, or 40 mg once daily) compared to placebo (each on top of stable background RA medication of weekly MTX), irrespective of treatment discontinuation or interruption due to

Objectives Estimand Description (Including Endpoint)

discontinuation or interruption for any reason.

tolerability issues or lack of efficacy, and as though no increase in any other RA medication.

Endpoint: Composite clinical response (Success/Failure) at Weeks 4 and 8 defined as achieving clinical response according to the criteria for ACR20 without discontinuing treatment due to tolerability issues or lack of efficacy or requiring any increase in RA medications.

Estimand 4: Difference in percentage of patients with moderate to severe active RA with a previous inadequate response to MTX alone, with confirmed intra-articular synovitis on baseline MRI, who would have a successful composite clinical response after each of 4 and 8 weeks of treatment with MBS2320 (5 mg, 20 mg, or 40 mg once daily) compared to placebo (each on top of stable background RA medication of weekly MTX). A successful composite clinical response is defined as achieving clinical response according to the criteria for ACR20 without discontinuing treatment due to tolerability issues or lack of efficacy or requiring any increase in RA medications, but irrespective of any interruptions required for treatment related reasons.

Other Secondary Objectives

To evaluate the efficacy of MBS2320 (5 mg once daily, 20 mg once daily, and 40 mg once daily) compared with placebo on other clinical endpoints in participants with active RA on stable background MTX who have had an inadequate response to MTX alone, with confirmed

Endpoints

- 1. Percentage of participants achieving clinical response according to the criteria for ACR50 at Weeks 4, 8, and 12;
- 2. Percentage of participants achieving clinical response according to the criteria for ACR70 at Weeks 4, 8, and 12;
- 3. Change in hsCRP level compared to baseline at Weeks 4, 8, and 12;
- 4. Change in TJC (68 joints) compared to baseline at Weeks 4, 8, and 12;

Objectives

Estimand Description (Including Endpoint)

intra-articular synovitis on baseline MRI.

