group participants according to the treatment they actually receive.

Full Analysis Set

The FAS will consist of all randomised participants whether or not they experienced significant protocol deviations affecting evaluations.

they experienced significant protocol deviations affecting evaluation of the endpoints. All analyses using the FAS will group participants

according to the randomised treatment.

Modified Full Analysis Set (mFAS) The mFAS will consist of all randomised and eligible participants with confirmed intra-articular synovitis on baseline MRI in FAS (grouped according to randomised treatment). The mFAS applies analysis flags to censor data after certain intercurrent events:

Flag P: Censors data after discontinuation or interruption of treatment for unrelated reasons (i.e. due to logistical issues or AEs due to an unrelated medical condition not considered to be due to treatment or the underlying RA disease) and resulting in >20% reduction in treatment administered during the approximately 4-week period since last visit. If treatment is resumed following an interruption, then subsequent data may be included provided at least 80% of treatment is taken during the previous 4-week period. This will be particularly useful for targeting Estimands 1 and 4.

Flag A: Censors data after discontinuation or interruption of treatment for any reason or any increase in RA medications and will be particularly useful for targeting hypothetical estimands (Estimands 2A and 3A). Only interruptions resulting in >20% reduction in treatment administered during the approximately 4-week period since last visit are considered relevant; for shorter interruptions, all resulting data are selected. If treatment is resumed following an interruption, then subsequent data may be included provided at least 80% of treatment is taken during the previous 4-week period.

Flag B: Censors data after discontinuation of treatment for unrelated reasons or any increase in RA medications and will be particularly useful for targeting the 'partially' hypothetical estimands (Estimands 2B and 3B). Interruptions for unrelated reasons are handled in the same way as Flag P.

Pharmacokinetics (PK) Set

The PK set will consist of all participants who receive at least 1 dose of MBS2320 and have at least 1 evaluable PK concentration. Analyses using the PK population will group participants according to treatment received.

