Statistical analysis will be performed using SAS software Version 9.4 or later. Continuous variables will be summarised using the mean, standard deviation, median, minimum value, and maximum value. Categorical variables will be summarised using frequency counts and percentages. Data will be listed in data listings.

Details of the statistical analyses, methods, and data conventions will be described in the statistical analysis plan (SAP). All statistical tests will be 2-sided and performed using a 5% significance level, leading to 95% (2-sided) confidence intervals (CIs), unless indicated otherwise.

Analysis of Primary Efficacy Endpoint

Main Estimation of Primary Efficacy Estimand 1

The primary efficacy estimand is the absolute difference between each of the 3 different doses of MBS2320 and placebo in the percentage of participants who would achieve successful composite clinical response at Week 12 (which assumes failure for those who have any increase in RA medications or treatment discontinuation due to lack of efficacy or tolerability issues). The primary efficacy estimand will be estimated using a logistic regression model and the delta method, with the stratification factors and treatment as factors using the mFAS (Flag P). Missing data will not be imputed and are assumed missing completely at random (MCAR).

Sensitivity Analysis of Primary Efficacy Estimand 1

In the sensitivity analysis of the primary efficacy estimand, multiple imputation (MI) assuming missingness at random (MAR) will be used to impute any missing component of the composite clinical response at Weeks 4, 8, and 12, and then to derive the composite

outcomes. The logistic model will be fitted to each multiply imputed data set and the estimates of difference in percentages and standard error (SE) from the delta method will be pooled using Rubin's method. The overall difference of each dose relative to placebo will be presented with *P* value.

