A reference-based multiply imputation model will be used to impute missing data after discontinuation of treatment due to related reasons (tolerability issues or lack of efficacy). As for Estimand 2A, the change from baseline in RAMRIS score will be derived on each multiply imputed data set and analysed using ANCOVA, and Rubin's method will be used to pool results.

Main Estimation of Secondary Efficacy Estimand 3A

A mixed model for repeated measures (MMRM) will be fitted to change from baseline at Weeks 4, 8, and 12 as the dependent variable and including fixed effects for DAS28-hsCRP baseline covariate, treatment, visit, treatment by visit interaction, and the stratification factors. An unstructured covariance will be used to model the covariances over time on participants. The least squares mean change from baseline in DAS28-hsCRP and differences relative to placebo with 95% CI and *P* value will presented at each time point.

Missing data are assumed to be MAR in the MMRM, which is well suited to estimate this type of hypothetical estimand.

Main Estimation of Secondary Efficacy Estimand 3B

Similar estimation (via MMRM) as described for Estimand 3A will be conducted for Estimand 3B. Note that this requires participants who discontinue treatment to return at Week 12 for assessment. Missing data are assumed to be MAR, which is unlikely to hold in the case of dropouts following discontinuation of treatment.

A sensitivity analysis will be conducted for Estimand 3B, using a reference-based MI model to impute missing data after discontinuation due to related reasons. The change from baseline

in DAS28-hsCRP will be derived on each multiply imputed data set and analysed using MMRM, and Rubin's method will be used to pool results.

Main Estimation of Secondary Efficacy Estimand 4

The estimation of Estimand 4 is similar to that described for Estimand 1. A logistic model will be fitted to successful composite clinical response at each of Weeks 4 and 8 including the stratification factors and treatment (qualitative) as factors; missing data will not be imputed and assumed MCAR.

In a sensitivity analysis, an MI model will be used to impute any missing components of the composite clinical response at Weeks 4, 8, and 12. Logistic model will be fitted to each multiply imputed data set and Rubin's method use to pool results. The overall difference of each dose relative to placebo will be presented with *P* value, at each time point.

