Additional sensitivity analysis of the successful composite clinical response at Weeks 4, 8, and 12 will be performed using Logistic Generalized Linear Mixed Model with fixed effects for treatment, visit, treatment by visit interaction, and the stratification factors. More details will be provided in the SAP.

Analyses of Other Efficacy and Exploratory Endpoints

The other efficacy endpoints will be analysed descriptively, based on the mFAS (Flag B), except for ordinal endpoints (e.g. ACR50 & ACR70) which will be analysed based on mFAS (Flag P). Sensitivity analysis may be undertaken; details will be provided in the SAP.

The exploratory efficacy endpoints will be analysed descriptively, based on the mFAS (with no flags applied) and the mFAS (Flag A). Sensitivity analysis may be undertaken; details will be provided in the SAP.

Analysis of Pharmacokinetic Endpoints

MBS2320 and MBS2473 plasma concentrations will be determined in pre-dose samples at Weeks 4 and 12, postdose samples collected 3 (± 1) hours following last dose at Week 12, and at EOS.

Plasma concentration of MBS2320 and MBS2473 (where applicable) will be determined for each sample, excluding placebo controls.

All MBS2320 and MBS2473 plasma concentration data will be listed by participant and visit/sampling time point and summarised by administered treatment.

SAS® software Version 9.4 or higher (SAS Institute, Inc, Cary, North Carolina) will be utilised for the generation of any tables, listings, and figures.

Analyses of Safety

The incidence of treatment-emergent AEs for the safety population will be summarised by treatment group. Adverse events will be coded using the Medical Dictionary for Regulatory Activities to classify events under primary system organ class and preferred term. Adverse event data will be presented in incidence tables. Adverse events will also be summarised by severity, seriousness, and relationship to IP for each treatment group. Data will also be listed in data listings.

The incidence of laboratory abnormalities by type, frequency, and severity will be summarised by treatment groups. Change from baseline in continuous laboratory variables will be summarised by visit and treatment groups.

All other safety variables (including vital signs and ECGs) will be summarised by treatment group and visit.

Other Analyses

Summary statistical analyses will be provided for demographics, medical history, and physical examination, and ophthalmological assessments at baseline.

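### The continuous other secondary endpoints get only available-case arm summaries after Flag B censoring; the Estimand 3B model would give a baseline-adjusted difference from placebo with an interval at little cost

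*Combined protocol and SAP*

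**What the plan says.** - **Objective.** Other Secondary Objectives sets out to evaluate efficacy "compared with placebo on other clinical endpoints in participants with active RA on stable background MTX". Endpoints 4-8, 10, 11 and 17-19 (joint counts, pain, the global assessments of disease activity and health, RAID, FACIT-F, HAQ-DI, EQ-5D) are changes from baseline at Weeks 4, 8 and 12. Endpoint 20 (CARLOS) is a change from baseline to Week 12 only.
- **Analysis rule.** "The other efficacy endpoints will be analysed descriptively, based on the mFAS (Flag B". Ordinal endpoints, with ACR50 and ACR70 as examples, move to Flag P. The rule ends: "Sensitivity analysis may be undertaken; details will be provided in the SAP".
- **Meaning of descriptive.** Statistical Methods: "Continuous variables will be summarised using the mean, standard deviation, median, minimum value, and maximum value".
- **Flag B.** "Censors data after discontinuation of treatment for unrelated reasons or any increase in RA medications". Unrelated interruptions are treated as under Flag P, so they count when they cut dosing by more than 20% since the last visit. Values after stopping for tolerability or lack of efficacy are kept.
- **DAS28-hsCRP with the same flag.** "Similar estimation (via MMRM) as described for Estimand 3A will be conducted for Estimand 3B". The 3A model has baseline, treatment, visit, treatment by visit and the stratification factors. It reports least squares mean differences from placebo with 95% CIs.

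**The concern.** The plan says Flag B is meant for Estimands 2B and 3B, which ask what would have been seen had RA medication not been increased. Censoring alone does not give that quantity; something must stand in for the removed values. The plan does this for RAMRIS (multiple imputation, then ANCOVA) and for DAS28-hsCRP (MMRM). For the continuous other secondary endpoints it censors and then averages what is left.

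An available-case mean is free of bias only if the removed values are a random subset. The Sample Size section describes increases in RA medication as a consequence of worsening disease, so at least part of the censoring is informative.

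Three things are at stake. The arm means may be too favourable. The gap between arms may be distorted. And no estimate of the difference with its precision is produced for endpoints that include most components of the primary ACR20 response as well as fatigue and quality of life. The 28-joint counts in DAS28-hsCRP come from the same joint assessments as endpoints 4 and 5, so two tables built on related data could disagree for reasons of method alone.

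**Working it through.** The plan states no figure for these endpoints, so there is none to reproduce. It gives no rate of RA-medication increase and no correlations, so the sizes below rest on assumptions.

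**1. Inputs**
- From the documents: visits at Weeks 4, 8 and 12, the Flag B rule, and 45 evaluable per arm (Sample Size).
- Assumed: outcome SD 1; true differences 0.30, 0.425 and 0.50 SD at Weeks 4, 8 and 12; placebo improvement 0.4, 0.5 and 0.6 SD; baseline to post-baseline correlation 0.4-0.6; between-visit correlation 0.6-0.75.
- Assumed censoring: after Week 4 or Week 8, logit P(event) = a + 2 × change from baseline in SD (higher = worse). All later values are removed.

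**2. Week 12 result when poor response is commoner on placebo** (correlations 0.5 and 0.7, large simulated samples; loss = 1 − raw/true)

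| Poor-response events | a | Censored, placebo / active | True | Raw | Loss | Mean too good by (SD), placebo / active |
|---|---|---|---|---|---|---|
| All censored | −4.0 | 6.5% / 3.7% | 0.502 | 0.473 | 6% | 0.07 / 0.04 |
| All censored | −3.0 | 13.0% / 8.0% | 0.502 | 0.455 | 9% | 0.13 / 0.09 |
| All censored | −2.2 | 20.9% / 13.8% | 0.498 | 0.435 | 13% | 0.20 / 0.14 |
| All censored | −1.8 | 25.8% / 17.6% | 0.498 | 0.426 | 14% | 0.25 / 0.18 |
| Half kept | −4.0 | 3.2% / 1.9% | 0.501 | 0.488 | 3% | 0.03 / 0.02 |
| Half kept | −3.0 | 6.6% / 4.0% | 0.501 | 0.480 | 4% | 0.06 / 0.04 |
| Half kept | −2.2 | 10.4% / 6.9% | 0.498 | 0.473 | 5% | 0.09 / 0.07 |

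'Half kept' treats half of the poor-response events as discontinuations whose later values Flag B retains; the one-half is an assumption. Over the other correlations, the heaviest setting (24-28% of placebo and 15-19% of active censored) gave raw differences of 0.42-0.43. The upper end is (0.50 − 0.42)/0.50 = 16%. The working range is therefore about 3-16% for placebo censoring of 3-28%.

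**3. Direction.** This used a separate set-up: a 0.77 SD effect, which is the latent-normal shift implied by 35% v 65% response, Φ⁻¹(0.65) − Φ⁻¹(0.35) = 0.771, with exactly the worst responders censored.
- Equal censoring, 10% in each arm: raw 0.771, true 0.771. Both arm means are still 0.135 SD too good (about 0.24 SD at 20% in each arm).
- More on active, 5% placebo and 10% active: raw 0.833, true 0.772. The difference is now 8% too large.
- More on placebo: the loss ran from 5% (5% v 2%) to 28% (30% v 10%). This harsher rule shows how far the size depends on assumption, and I do not use it for the range.

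**4. Precision, with no censoring.** Per-participant variance is 2(1 − ρ) for raw change and 1 − ρ² after baseline adjustment, so the SE ratio is √[2/(1 + ρ)]. This gives 1.20, 1.15 and 1.12 for ρ = 0.4, 0.5 and 0.6. At 45 per arm and ρ = 0.5, the SEs are √(1 × 2/45) = 0.211 and √(0.75 × 2/45) = 0.183. A 12-20% larger SE thus comes from ignoring baseline, whatever the censoring.

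**5. Model under MAR.** A sequential regression on baseline and earlier visits, the likelihood analogue of the MMRM, returned the true difference in every setting of step 2. It had to, because events there depend only on observed values.

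**The case against.** - **Descriptive reporting of lower-tier phase 2b endpoints is legitimate.** No estimand is defined for them. The phrase 'compared with placebo' also appears in the safety objective, which is summarised descriptively too, so the wording alone does not promise a model. This stands, and it is why the point is an improvement and not an error.
- **The text is a synopsis that defers detail to the SAP.** True, but what it defers for these endpoints is an optional, unspecified sensitivity analysis. The main rule is stated.
- **The remaining set is not simply the participants whose RA medication was never increased.** A reader might infer that it is. Flag B also removes unrelated discontinuations and relevant interruptions, and it keeps some of the worst-doing participants. With half of the poor-response events kept, the loss is only 3-5%.
- **Increases may be rare.** Inclusion criterion 4 asks for stable MTX throughout a 12-week treatment period. At the lowest fully censored setting the bias is 0.03 SD, about one-seventh of the raw SE (0.03/0.211).
- **The MAR model is no guarantee.** Under Estimand 3B the plan itself doubts MAR for dropouts after discontinuation. The simulated recovery holds by construction.
- **CARLOS does not fit.** It has no Week 4 or 8 value, so none of the simulation applies. It is also a 9-point scale and might be read into the open-ended ordinal exception.

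**Conclusion.** The point holds as a cheap improvement. For the ten repeated continuous endpoints the planned summaries are available-case means after partly informative censoring, and they tend to look better than the quantity Flag B is meant to target. If RA medication is increased more often on placebo, the apparent difference shrinks by about 3-16%, given assumed placebo censoring of 3-28% and the correlations above. The lack of a baseline-adjusted difference with an interval does not depend on any of these assumptions.

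Two stronger readings are tempting and not supported. One is that the rule necessarily favours placebo: the documents give no rate by arm, equal rates leave the difference unbiased, and a higher rate on active reverses the bias. The other is that dose selection will be misled: no section says that these endpoints will be used to choose a dose.

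The point does not cover the scale of hsCRP, the global impression of change or the response-rate endpoints, and it does not touch the primary analysis.

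**What to change.** Amend the rule for the continuous other efficacy endpoints.

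- **Endpoints 4-8, 10, 11 and 17-19:** fit the Estimand 3B MMRM on mFAS (Flag B), with the endpoint's own baseline, treatment, visit, treatment by visit and the stratification factors, and unstructured covariance. Report each dose-placebo least squares mean difference at Weeks 4, 8 and 12 with a 95% CI labelled nominal, and no P value.
- **Censoring:** tabulate the number of participants censored by arm and visit, so that the direction and likely size of any bias can be judged.
- **Assumption:** state that MAR is doubtful for dropouts after discontinuation, as the plan already does for Estimand 3B.
- **CARLOS:** state that it follows Flag B, and use ANCOVA with baseline CARLOS and the Estimand 2B imputation route. Say that this corrects informative censoring less well, because there is no intermediate on-treatment value.
- **Raw arm summaries:** keep them as supporting tables.

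The cost is a few sentences in the SAP and re-use of code already needed for Estimands 2B and 3B, with no new data or visits. The downside is 10 endpoints × 3 doses × 3 visits = 90 nominal intervals (counting EQ-5D as one score), plus 3 for CARLOS. None of them may be read as confirmatory.
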